Medication data are collected from both patient report and clinic validated health record check. The primary outcome data source will be the clinic validated health record check that the medication was currently prescribed. For patients who die or discontinue from the study before their last planned follow-up, sites will be instructed to enter medication prescriptions at the last time the patient was stable.

The primary outcome will be analyzed using a mixed-effects model repeated measures (MMRM) multivariable logistic regression model with random intercept for the site to account for the clustering effect, an unstructured covariance for repeated-measures overtime, an interaction for treatment by time, as well as adjustment for potential baseline factors as covariates including the baseline composite score (see Appendix 1, Section 8.1 for list). Time is modeled as a categorical variable, which allows for an arbitrary trajectory. The interaction of treatment and time allows for different patterns of change by treatment overtime. All outcome data are used regardless of whether a patient has complete data. This model will provide the estimated adjusted odds ratio (that is odds of achieving a composite score of 3 at follow-up in the intervention arm to the similar odds in the usual care) and 95% confidence interval (CI). Intra-cluster correlation coefficients (ICCs) will be calculated from unadjusted and adjusted models overall and by treatment arms to quantify within-cluster heterogeneity.

Mixed model for the i th subject:

$$\text{Logit } E[Y_i] = X_i\beta + Z_i\gamma_i + \varepsilon_i$$

Where γ_i is independent of ε_i and both are normally distributed with mean zero and variance G and R_i , respectively. Y_i is the $n_i \times 1$ response vector for the n_i observed responses for the i^{th} patient. β is the $p \times 1$ fixed-effects vector; X_i is the $n_i \times p$ fixed-effects design matrix; Z_i is the $n_i \times q$ matrix of random-effects design matrix; γ_i is the $q \times 1$ vector of random effects and ε_i is the $n_i \times 1$ vector of residuals. G is the $q \times q$ covariance matrix for the random effects, and R_i is the $n_i \times n_i$ covariance matrix for the residuals, which accounts for the repeated measurements. The only random effect is for cluster.

Example SAS code* with data in one record per patient per outcome time point:

```
proc glimmix data=indata;
  class futime intervention sitenum subnum &otherclass / ref=first;
  model defectfreescorefu (event='1') = futime intervention futime*intervention &othercovar
    / dist=binary link=logit s ddfm=betwithin;
  random intercept / subject=sitenum;
  random futime / subject=subnum(sitenum) type=un residual;
  nloptions tech=nr ridge;
run;
```

*Modifications to SAS code may be necessary pending model fit and/or convergence issues.

As a sensitivity analysis, we will assess a variation of the composite score where the acceptable alternative of metformin monotherapy with HbA1c<7 in component one is not considered part of the outcome.

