 - Meet with the clinic leadership pair (cardiologist and endocrinologist/diabetes care specialist) and the research coordinator. The clinical leadership pair, research coordinator, patient advocate, and study staff (for prior authorizations and patient education) will constitute the core study team at each clinic site, and
 - Respond to the clinic's current practice, care processes, and available outcomes data from the site survey, and help the clinic team develop a GAP analysis. This GAP analysis will be specific to each site. Each site will formally submit this GAP analysis within 2 weeks of site visit to the DCRI Project Lead.
- The COORDINATE-Diabetes Trio assigned to each clinic site will work with the clinic site study team to establish the final Clinic Action Plan. This Clinic Action Plan will be largely based on the Standard Manual of Operations developed by the COORDINATE-Diabetes study team, but may include some site-specific adaptations as deemed necessary by each site team. The implementation of any adaptations and their content will be recorded in the study database.
- Clinic healthcare providers will receive disease specific and study implementation training (Qualtrics Modules).

Specific Educational Intervention site activities conducted by the COORDINATE-Diabetes staff will include:

- Building a multidisciplinary clinic site team (cardiology and endocrinology/diabetes care specialist leadership pair, site research coordinator, patient advocate, staff for prior authorization and patient education)
- Conducting clinic-level education related to trial protocol, 2019 ADA guidelines^{5, 6}, 2013 ACC/AHA guidelines for management of blood cholesterol⁹, data from recent cardiovascular outcomes trials in diabetes, safety education related to prescribed medications (example, hypoglycemia, DKA), and FDA label indications for relevant medications.
- Conducting clinic-level education related to drug safety, including statin side effects and potential side effects of anti-diabetes medications with CV benefit (such as hypoglycemia, DKA, etc).
- Helping site teams refine and implement a care pathway for managing diabetes and CV risk factors.

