7.2 Randomization

Site randomization: Site will be randomized when eligibility to participate in the trial has been established. To minimize imbalance between population characteristics in the basic education and intensive educational intervention groups, a stratified randomization based on geographic classification (urban or non-urban) will be implemented to ensure that selected site characteristics are balanced within each stratum. Site randomization will be conducted through a database platform using the randomization scheme (block randomization based on stratification factors) generated by the study statistician and uploaded by data management. Site management has a "button" on their web portal that they can select when a site is ready to be randomized (must have IRB approval and contract executed). Randomized site will receive an official email with their randomization status/assignment.

Mitigation of potential sample bias after site randomization

CONFIDENTIAL

The following processes will be implemented:

- Education before randomization, after randomization, and throughout the enrollment process that sites should AVOID enrolling only a certain type of patient (i.e., either high-or low-risk only)
- Assessment of patient enrollment characteristics once 25% and 50% of patients have been enrolled in the trial overall and by site to ensure that baseline characteristics are similar in the basic education arm and intensive educational intervention arm. If an imbalance is observed, measures will be taken to visit the involved sites and remedy the issue with the on-site clinical leads.
- Outcomes will be adjusted for differences in baseline characteristics, to be detailed in the statistical analysis plan.

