1.3 Sample Size Justification

The primary outcome is the proportion of patients achieving guideline-recommended therapy, defined as a composite score of 3 at the last follow-up visit. The primary analysis is based on the comparison of primary outcome between the basic education and intensive educational intervention arms. The sample size provides adequate power to detect a clinically meaningful effect size of at least a 10% difference between treatment arms in the proportions of patients achieving a composite score of 3 by the last follow-up visit.

In this cluster-randomized trial, where the experimental unit is site, the effective sample size and power is impacted by intra-cluster correlation (ICC). For the primary outcome, the sample size calculation is based on the ability to detect at least a 10% difference between treatment arms in the proportion of patients achieving guideline-recommended management for T2DM and CVD with composite score of 3. The effect size of a 10% change has been chosen as a clinically meaningful difference between the intensive educational intervention and basic education arms.

A minimum of 42 sites (“clusters”) with an average cluster size of 25 patients per site (a total of 1050 patients) will provide at least 85% power to detect a 10% difference in the primary outcome between educational intervention arms through the last follow-up visit (6 to 12 months). This estimate of a minimum of 21 sites per arm (average of 25 patients per site) is based on the assumption of 10% of patients in the basic education arm, and at least 20% in the intensive educational intervention arm, receiving guideline-recommended therapy at the last follow-up visit, with an intra-correlation coefficient (ICC) of 0.05, and two-sided type I error rate of 0.05. The sample size/power calculations were carried-out using R function “n4props” in (package “CRT Size”).¹

2. General Considerations for Data Analysis

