9.1 Potential Adjustment Variables for Primary Outcome Model

Variable	Variable Type
Intervention	yes/no
Site: Urban vs. non-urban	yes/no
Age	continuous
Male sex	yes/no
Race	categorical (Black, Asian/Other, vs. White)
Baseline composite score	ordinal (0-2)

Charlson Comorbidity Index (CCI)	categorical (severe defined as CCI scores ≥ 5 , moderate defined as CCI scores of 3–4, vs. mild defined as CCI scores of 1–2)
Baseline systolic BP	continuous
Baseline diastolic BP	continuous

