9.2 Potential Adjustment Variables for Binary Intermediate Outcome Models

Variable	Variable Type
Intervention	yes/no
Site: Urban vs. non-urban	yes/no
Age	continuous
Male sex	yes/no
Race	categorical (Black, Asian/Other, vs. White)
Baseline composite score	ordinal (0-2)
Charlson Comorbidity Index (CCI)	categorical (severe defined as CCI scores ≥ 5 , moderate defined as CCI scores of 3–4, vs. mild defined as CCI scores of 1–2)
**Achievement of Baseline HbA1c < 8%	yes/no
Achievement of Baseline systolic BP < 130 mmHg	yes/no
Achievement of Baseline diastolic BP < 80 mmHG	yes/no
**Achievement of Baseline LDL-C < 70 mg/dL	yes/no
Interaction* between intervention and achievement of baseline target	combination of intervention (yes/no) and achievement of baseline target (yes/no)

*For each outcome, we will test for interaction between intervention and achievement of that baseline target.

**Only the HbA1c and LDL-C outcomes will be adjusted for achievement of these Baseline metrics due to the rate of not drawn for these labs.

10. Appendix 2: Table Shells

Table 1. Patient-level Baseline characteristics by Intervention

PATIENT CHARACTERISTICS	Intervention	Usual Care
Age		
Sex		
Race: White Black Asian Other		
Ethnicity: Hispanic/Latino Not reported		
Insurance/payer: Medicare Part D Supplemental Plan Medicaid Private State-specific (non-Medicaid) Military health care Indian health services Other US insurance		
Medication prescription:		
Lipid lowering therapy: Statin: Low intensity Moderate intensity High intensity Ezetimibe Fibrate Niacin PCSK-9 Prescription-grade Omega 3 FA		
Glucose-lowering therapy: Metformin Insulin Sulphonylurea DPP4 Thiozolidinedione GLP-1RA SGLT-2		

Other Severity: Monotherapy > 1 glucose-lowering medication Average insulin dose		
Anti-hypertensive therapy ACE/ARB Beta-blocker Diuretic Calcium channel blocker MRA		
Anti-thrombotic therapy Aspirin P2Y12 receptor antagonist Warfarin DOAC		
Cardiovascular history		
Coronary artery disease Prior MI Prior CABG Prior PCI Obstructive ($\geq 50\%$) CAD (CT/ICA)		
Cerebrovascular disease: Prior ischemic stroke Carotid artery stenosis ($> 50\%$)		
Peripheral arterial disease: Prior peripheral revascularization Prior amputation due to poor circulation History of Claudication with ABI < 0.9		
Atrial fibrillation		
Heart failure		
Hypertension		
Dyslipidemia		
Cigarette smoking		
Non-Cardiovascular		
Charlson Index		
Diabetes history		
Time since diabetes diagnosis < 1 year		

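### The primary model's covariate list omits insurance/payer, leaving a small, conditional exposure to payer selection by clinics that already know their arm

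*SAP*

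**What the plan says.** SAP 3.1 specifies a repeated-measures logistic model with a random intercept for site, "as well as adjustment for potential baseline factors as covariates including the baseline composite score (see Appendix 1, Section 8.1 for list"). The pointer is wrong: Section 8 of the SAP holds the references, and the list stands in 9.1, headed "Potential Adjustment Variables for Primary Outcome Model". Besides intervention it contains urban/non-urban location, age, sex, race, baseline composite score, Charlson index, and systolic and diastolic blood pressure. SAP 3.2.1 uses the same list for the secondary medication outcomes.

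Payer appears in SAP Appendix 2, in the patient-level Table 1 shell by arm: "Insurance/payer: Medicare Part D Supplemental Plan Medicaid Private State-specific (non-Medicaid") and further classes. Table 3 of the Protocol, which sets out patient-level data collection, does not name it.

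Four other provisions bear on the point:
- **Order of events.** Protocol section 2: the study is open-label, and each clinic enrols its patients after it has been randomized.
- **Intensive-arm team.** Protocol 4.2 includes "staff for prior authorization and patient education", and sends intensive sites monthly reports on enrolled patients' progress toward the primary outcome.
- **Selection safeguards.** Protocol 7.2 tells sites not to enrol only one type of patient, checks enrolment characteristics at 25% and 50% of enrolment with site visits if arms differ, and states: "Outcomes will be adjusted for differences in baseline characteristics, to be detailed in the statistical analysis plan".
- **Reporting of imbalance.** SAP 2.1 reports patient-level standardized differences. No rule links them to the model.

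**The concern.** Clinics know their arm when they choose patients, and intensive clinics also know the measure on which they receive feedback. The Protocol treats selection after randomization as a real possibility. Insurance coverage is a plausible influence on whether a drug is prescribed and stays prescribed, and prior-authorization staffing suggests that the trial team regarded payer approval as a practical matter.

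If intensive clinics tended to enrol better-covered patients, part of the resulting difference in prescribing would be credited to the intervention. As written, the SAP would show the difference in Table 1 and leave it out of the model. Adding payer only after seeing that table would look data-driven, so the decision belongs in the plan before database lock.

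**Working it through.** **1. The plan's own figure.** Inputs from SAP 1.3: 21 sites per arm, 25 patients per site, "assumption of 10% of patients in the basic education arm, and at least 20% in the intensive educational intervention arm", "with an intra-correlation coefficient (ICC) of 0.05, and two-sided type I error rate of 0.05"; the claim is that this "will provide at least 85% power to detect a 10% difference in the primary outcome".
- Design effect: 1 + (25 − 1) × 0.05 = 2.2.
- Effective patients per arm: 525 / 2.2 = 238.6.
- SE of the difference: sqrt((0.10 × 0.90 + 0.20 × 0.80) / 238.6) = 0.0324, and 0.10 / 0.0324 = 3.09.
- Power: 87.1% (normal, unpooled), 86.7% (normal, pooled), 85.4% (noncentral t, 40 df).

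The stated 85% reproduces. The formula uses no covariates, so adding payer leaves it unchanged. The design odds ratio is (0.20/0.80) / (0.10/0.90) = 2.25.

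**2. Size of a payer distortion.** The documents give no payer figures, so these inputs are assumptions: half of basic-arm patients have favourable coverage, marginal success is 10%, the intervention has no true effect, and other covariates capture none of the payer difference. For a payer odds ratio R, find stratum rates p0 (less favourable) and p1 (favourable) with 0.5·p0 + 0.5·p1 = 0.10 and odds(p1)/odds(p0) = R. With d extra favourable share in the intensive arm, its success rate is 0.10 + d(p1 − p0).

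| R | p0, p1 | d | Intensive-arm rate | Spurious OR |
|---|---|---|---|---|
| 2 | 6.97%, 13.03% | 10 points | 10.61% | 1.068 |
| 2 | 6.97%, 13.03% | 20 points | 11.21% | 1.137 |
| 3 | 5.39%, 14.61% | 10 points | 10.92% | 1.103 |
| 3 | 5.39%, 14.61% | 20 points | 11.84% | 1.209 |

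With R = 1.5 and d = 5 points the odds ratio is 1.02. These are marginal odds ratios; the SAP model's are conditional on site and covariates, so they show scale only.

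**3. Effect on the test.** The null SE at 10% in both arms is sqrt(2 × 0.10 × 0.90 × 2.2 / 525) = 0.0275. Two-sided rejection under a bias b is Φ(b/SE − 1.96) + Φ(−b/SE − 1.96). For 10 points of imbalance (b = 0.6 to 0.9 points) it is 5.6% to 6.3%. For 20 points (b = 1.2 to 1.8 points) it is 7.3% to 10.3%. The nominal level is 5%.

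**4. How much imbalance chance would produce.** SD of the between-arm difference in payer share = sqrt(2 × 0.25 × (1 + 24 × ICC) / 525). At an assumed payer ICC of 0.05, 0.10 and 0.20 this is 4.6, 5.7 and 7.4 points. A 10-point difference is therefore 1.3 to 2.2 SDs, within the reach of chance. A 20-point difference is 2.7 to 4.4 SDs, and would in practice need strong selection.

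**The case against.** The case for leaving the list alone has six parts.

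- **Chance imbalance is not bias.** Payer differences between randomly allocated clinics are between-site variation, and the random intercept and design ICC carry that into the standard error. This stands: type I error averaged over randomizations is preserved. The argument for adjustment rests on systematic selection, and on the conditional point that an imbalance actually seen shifts that trial's estimate. The random intercept removes neither.
- **Protocol 7.2 has other safeguards.** Site education and the two enrolment checks address selection directly. They lower its likelihood, but the stated response is a site visit, which does not correct for patients already enrolled.
- **The outcome is prescribing.** SAP 3.1 counts a current prescription in the health record, not a filled one. This weakens the path without closing it, because coverage can affect whether a prescription is written or continued.
- **Payer is one of several omitted Table 1 rows.** HbA1c, eGFR and diabetes duration are also absent from 9.1. That is fair; the documents do not rank payer above them. Prior-authorization staffing gives payer a specific rationale, but the Protocol does not link those staff to payer class or to the first component of the score.
- **Other covariates may absorb part of it.** Age, race, location and baseline score could do so, which makes the figures above upper values for their inputs. None of them measures coverage.
- **Adjustment is not free.** A payer covariate changes the conditional odds ratio slightly and need not reduce its standard error. Broad payer class is also only a proxy for drug coverage.

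A reader might infer that the primary odds ratio is biased by payer, or that the SAP breaches Protocol 7.2. The documents support neither. They report no payer imbalance, and Protocol 7.2 defers details to the SAP, which does pre-specify a list. Nor should the effect of prior-authorization support be adjusted away: it is part of the intervention. Only baseline payer mix is a candidate confounder.

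**Conclusion.** The omission is real and the concern is modest. Payer is planned for tabulation but absent from the primary covariate list, in a design where unblinded clinics choose patients after randomization, and nothing in the SAP brings an observed payer difference into an analysis.

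Under the stated assumptions the distortion is 0.6 to 0.9 percentage points for a 10-point imbalance and 1.2 to 1.8 points for 20 points, against a 10-point design difference. It could not plausibly create an effect of the size the trial was designed to detect, and would matter mainly for a result near the significance boundary. Every payer input is assumed, so these figures show scale and are not an estimate of bias in this trial.

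**What to change.** 1. Confirm that payer is captured at baseline for every patient in both arms. The SAP table shell implies that it is, but Protocol Table 3 does not list it. That silence is not decisive, since Table 3 also omits the medical history that the Charlson index needs.
2. Before database lock, add a collapsed payer class to list 9.1 (for example Medicare, Medicaid or state, private, other) for the primary model and the secondary medication models that share the list. At minimum, pre-specify a payer-adjusted sensitivity analysis of the primary outcome.
3. State how patients with more than one payer are classified and how missing payer is handled. The shell's categories may overlap, and SAP 2.2 has no imputation rule for payer.
4. Correct the reference from Section 8.1 to 9.1, and likewise the 8.2 reference in SAP 3.2.2 to 9.2.

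The cost is SAP wording, a category mapping, a missing-value rule and about three parameters. At the design rates about 525 × 0.10 + 525 × 0.20 = 157.5 successes are expected, which supports them comfortably.

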3.2 Secondary Endpoints

All of the following secondary outcomes will be assessed at or through last follow-up.

3.2.1 Guideline Recommended Management Endpoints

Secondary study objectives include assessment of the effect of the intervention on cardiologist provider behavior as measured by the individual components of the primary outcome and a variation of the primary outcome. We will also assess the effect of the intervention on the individual components of the primary outcome and a variation of the primary outcome by any provider. For each outcome listed below, we will determine whether the proportion of patients will be higher in the intervention than in the usual care arm. The secondary outcomes will be analyzed using the same methods as the primary outcome; a mixed-effects repeated measures logistic regression model with random intercepts for site to account for the effect of clustering, an unstructured covariance for repeated-measures overtime, an interaction for treatment by time, as well as adjustment for potential baseline factors as covariates including the baseline composite score (see Appendix 1, Section 8.1 for list). Given relatively a large number of pre-specified secondary components below, the 95% CIs on the ORs will be used in the interpretation of these findings, rather than p-values.

Guideline Recommended Management as Prescribed by Cardiologist Endpoints

- Proportion of patients prescribed by Cardiologist achieving guideline-recommended therapy for T2DM
- Proportion of patients prescribed by Cardiologist an ACEi/ARB treatment
- Proportion of patient prescribed by Cardiologist a high-intensity statin treatment
- Proportion of patients achieving a composite score of ≥ 2 prescribed by Cardiologist

Guideline Recommended Management by any Provider Endpoints

- Proportion of patients achieving guideline-recommended therapy for T2DM
- Proportion of patients an ACEi/ARB treatment
- Proportion of patient a high-intensity statin treatment
- Proportion of patients achieving a composite score of ≥ 2

